- i. Participants randomized to etanercept will receive an etanercept dose weekly from Week 0 through Week 15. Participants will have the option of returning to the study site weekly for dose administration or the option to self-administer at home for the weeks when no regular site visit is scheduled (ie, Weeks 1, 2, 3, 5, 6, 7, 9, 10, 11, 13, 14, and 15). Participants who decide to administer etanercept at home will record study drug administration information on a paper questionnaire. Participants randomized to etanercept will then have the option to initiate a weight-based guselkumab dose regimen with injections at Week 20 and 24 followed by q8w administration through Week 48 or terminate study participation after a study termination visit at Week 28.
- j. PASI 90 responders withdrawn from treatment at Week 16 who have not met loss of response criteria prior to Week 52 and are continuing into the long-term extension of the study will receive guselkumab at Week 52 followed by q8w administration beginning at Week 60 in the long-term extension. Participants withdrawn from treatment at Week 16 who met loss of response criteria prior to Week 48 and received a guselkumab dose at Week 48 and continue into the long-term extension will receive their next administration of guselkumab at Week 60 followed by q8w thereafter. Participants who meet loss of response criteria at Week 48 will receive a weight-based dose of guselkumab at Week 48 followed by a dose at Week 52 and q8w administration starting at Week 60.
- k. Vital signs include heart rate, blood pressure, and temperature.
- l. Girls of childbearing potential must have a negative urine pregnancy test before randomization and at all study visits through Week 16. After Week 16 a negative urine pregnancy test is required at all visits at which study intervention is to be administered.
- m. Head circumference will be measured for participants  $\geq 6$  to  $< 12$  years of age
- n. Pain experienced with each placebo or guselkumab injection will be assessed at each study visit at which an injection is administered. Pain will be assessed using the Faces Pain Scale-Revised for injection pain in children  $\geq 6$  to  $< 12$  years of age (Appendix 17 [Section 10.17]), and the linear Injection Pain Visual Analog Scale for adolescents  $\geq 12$  to  $< 18$  years of age (Appendix 18 [Section 10.18]).

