Participants randomized to guselkumab or placebo will receive a weight-based dose of study intervention at Weeks 0, 4, and 12. Participants randomized to etanercept will receive a weight-based etanercept dose up to 50 mg SC weekly through Week 15. Participants randomized

to etanercept will be given the option to self-administer or have their caregiver administer at home or have the study intervention administered at the study site.

At Week 16:

- Participants initially randomized to guselkumab will be treated as follows:
  - PASI 90 responders at Week 16 will not receive any additional doses of guselkumab until they lose  $\geq 50\%$  of their Week 16 PASI response, at which time they will be retreated with guselkumab followed by a dose 4 weeks later, and then guselkumab q8w thereafter through Week 52.
  - PASI 90 nonresponders at Week 16 will receive a placebo injection at Week 16 to maintain the blind and continue treatment with guselkumab q8w from Week 20 through Week 52.
- Participants initially randomized to placebo will be treated as follows:
  - PASI 90 responders at Week 16 will not receive any additional doses of study intervention until they lose  $\geq 50\%$  of their Week 16 PASI response, at which time they will initiate treatment with guselkumab SC followed by a dose 4 weeks later, and q8w thereafter through Week 52.
  - PASI 90 nonresponders will initiate treatment with guselkumab at Weeks 16 and 20, and q8w thereafter through Week 52.
- Participants initially randomized to etanercept will receive their last administration of etanercept at Week 15. Irrespective of PASI response at Week 16, participants or their legally acceptable representative will be given the option, in consultation with the investigator, to initiate treatment with guselkumab at Week 20 followed by a dose 4 weeks later, and then q8w thereafter through Week 48, or discontinue from study intervention administration. This option allows for participants receiving etanercept who have not attained an adequate level of efficacy or have poor tolerance for weekly injections to switch to guselkumab.

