## 6. STUDY INTERVENTION

### 6.1. Study Interventions Administered

Designation	Product	
Investigational Medicinal Product(s)	Guselkumab Authorization status in the EU/EEA:	
	Authorized	
	Unauthorized	X
	Placebo Authorization status in the EU/EEA:	
	Authorized	
	Unauthorized	X
	Etanercept Authorization status in the EU/EEA:	
	Authorized	X
	Unauthorized	

Guselkumab or placebo will be administered SC using a sponsor-supplied, single use administration device. This will be either the CCI PFS assembled with the UltraSafe Plus™ Passive Needle Guard (PFS-U) device, designed to deliver a single, fixed dose of CCI, or a CCI. Identical devices containing placebo will be used to deliver a volume equivalent to that of active treatment for participants randomized to the placebo arm. Guselkumab will be supplied as a CCI solution of guselkumab in a single-use CCI or CCI PFS. The PFS-U is assembled with a PFS containing 1.0 mL of study intervention and the CCI.

Participants will receive a dose based on body weight. At each dosing visit, participant weight will be measured and the dose of guselkumab will be adjusted accordingly. Participants will receive 1 of the following dose levels depending on their weight:

- Weight <70 kg: CCI administered CCI
- Weight ≥70 kg: CCI administered using the PFS-U

Placebo for guselkumab will also be supplied in a PFS assembled with either the UltraSafe Plus™ Passive Needle Guard or the CCI. Participants who weigh <70 kg will receive 1 or 2 injections of either guselkumab or placebo with a volume(s) determined using the weight-based dose calculation for guselkumab. In Part 2 of the study, participants or their caregiver will be given the option to self-administer guselkumab at the study site. Participants must be ≥12 years of age to self-administer guselkumab.

Commercially available etanercept (25 mg powder and solvent for solution for injection and 50 mg prefilled syringes) will be supplied and administered subcutaneously based on body weight:

- <63 kg: 0.8 mg/kg once weekly using powder and solvent for solution for injection.
- ≥63 kg: 50 mg once weekly administered using a prefilled syringe.

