### *Week 0 to Week 16 (Placebo-Controlled Period)*

The guselkumab and placebo administrations will be administered by site personnel at the study site. Etanercept will be administered at the study site at Week 0. Subsequent weekly doses of etanercept through Week 15 may be administered at the study site or be self-administered at home by the participant or caregiver on weeks without a site visit. The dose regimens are as follows:

- **Group I:** Weight-based guselkumab dose up to CCI SC at Weeks 0, 4, and 12.
- **Group II:** Weight-based placebo for guselkumab dose administered SC at Weeks 0, 4, and 12.
- **Group III:** Weight-based etanercept dose up to 50 mg SC weekly through Week 15.

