4.4. Extent of Exposure

The exposure data will be summarized through Week 16, through Week 52, and through LTE. The number of active study agent injections, and the cumulative dose of study agent will be summarized by treatment group for the safety analysis set.

In addition, the number of subjects who were withdrawn and retreated with guselkumab after Week 16, and the number of subjects who initiated guselkumab after Week 16 will be summarized for Part 1.

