7. SAFETY

Safety will be assessed by summarizing the incidence and type of AEs and examining changes in laboratory parameters (hematology and chemistry), vital signs, and suicidal ideation and behavior.

In the safety analyses for Part 1, subjects who were randomized and received at least 1 (partial or complete) dose of study agent administration will be included and analyzed according to the treatment they actually received, regardless of the treatment assigned at randomization. No formal statistical comparison is planned.

For Part 2, the safety analyses will be performed for all subjects enrolled in Part 2 and treated.

For LTE, the safety analyses will be performed for all subjects entered in LTE and treated at or after Week 52.

Depending on the safety data categories, the cumulative safety data will be analyzed through different study periods which include but are not limited to through Week 16, through Week 52, and through the LTE as appropriate. Unless otherwise specified, tabular summaries of safety events for key study periods are in general presented as follows:

Summaries through Week 16 (placebo-controlled period in Part 1):

Safety data through Week 16 will be summarized by treatment groups:

- Placebo
- Guselkumab
- Etanercept

This allows between-group comparisons of safety between the guselkumab group, etanercept group and the placebo group based on similar follow-up period in each group.

Summaries through Week 52 in Part 1

Safety data through Week 52 will be summarized by treatment group defined as follows:

1. **Placebo → Guselkumab:** all subjects who were randomized to placebo at Week 0, started treatment with placebo only, and later crossed over to receive treatment with guselkumab. Only the safety events/measurements from these subjects that occurred on or after their first administration of guselkumab will be included in this group.

2. **Guselkumab:** all subjects who were randomized to guselkumab at Week 0 and were treated with guselkumab. All the safety events/measurements from these subjects that occurred beginning at Week 0 will be included in this group.
3. **Etanercept → Guselkumab:** all subjects who were randomized to etanercept at Week 0, started treatment with etanercept only, and later crossed over to receive treatment with guselkumab. Only the safety events/measurements from these subjects that occurred on or after their first administration of guselkumab will be included in this group.

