7.1. Adverse Events

The verbatim terms used in the CRF by investigators to identify adverse events will be coded using the Medical Dictionary for Regulatory Activities (MedDRA version xx). Any AE occurring at or after the initial administration of study agent through the end of the trial is considered to be treatment emergent. If the event occurs on the day of the initial administration of study agent, and either event time or time of administration are missing, then the event will be assumed to be treatment emergent. If the event date is recorded as partial or completely missing, then the event will be considered to be treatment emergent unless it is known to be prior to the first administration of study agent based on partial onset date or resolution date. All reported treatment-emergent adverse events will be summarized by MedDRA system organ class, preferred term, and actual treatment group. The numbers of subjects reporting at least 1 event of the following treatment emergent AE categories will be summarized.

- AEs
- Serious AEs (SAEs)
- AEs leading to discontinuation of study agent

- AEs by severity
- AEs by relationship to study agent
- Infections
- Serious infections
- Infections treated with oral or parenteral antimicrobial treatment
- Injection-site reactions

In addition to the summary tables, listings will be provided for subjects who:

- Had SAEs
- Had AEs leading to discontinuation of study agent
- AEs of psoriasis
- AEs of severe intensity
- Serum sickness-like reactions and anaphylactic reactions

These summary tables will provide the count and percentage of subjects with 1 or more of the specified AEs by treatment group. The AEs and infections will also be summarized by age group through Week 16 and through Week 52 for Part 1. To adjust for the different duration of follow-up among treatment groups, number of events per hundred subject-years of follow-up through Week 52 will also be provided for all AEs.

Any unfavorable or unintended sign that occurs at the injection site is an injection site reaction and will be recorded as an injection site reaction by the investigator on the eCRF. An infection is defined as any AE that was recorded as an infection by the investigator on the eCRF.

The treatment-emergent adverse events of psoriasis include any event of erythrodermic psoriasis, pustular psoriasis, guttate psoriasis, and worsening or exacerbation of psoriasis. A listing of these events will be provided.

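### Through Week 16, injection-site reactions are summarised per participant with no per-injection rate, although etanercept is given 16 times against 3 for guselkumab or placebo

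*SAP*

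**What the plan says.** SAP Section 7 summarises safety through Week 16 by placebo, guselkumab and etanercept, and gives this reason for reading across the columns: "This allows between-group comparisons of safety between the guselkumab group, etanercept group and the placebo group based on similar follow-up period in each group".

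SAP 7.1 sets the measure: "The numbers of subjects reporting at least 1 event of the following treatment emergent AE categories will be summarized". Injection-site reactions are one of the listed categories, and the tables give counts and percentages of participants by treatment group.

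The schedules differ. For etanercept, Protocol 1.3.1 (footnote i) states: "Participants randomized to etanercept will receive an etanercept dose weekly from Week 0 through Week 15"; Protocol 6.1 agrees: "Weight-based etanercept dose up to 50 mg SC weekly through Week 15". For the other two arms, Protocol 4.1 states: "Participants randomized to guselkumab or placebo will receive a weight-based dose of study intervention at Weeks 0, 4, and 12". One dose can mean more than one needle. Protocol 6.1 says "Participants who weigh <70 kg will receive 1 or 2 injections of either guselkumab or placebo", and has the same one-or-two rule for etanercept below 63 kg.

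The SAP does take exposure into account. SAP 7.1 accepts that safety has to be read against exposure, and puts average weeks of follow-up and average number of administrations into most adverse event tables. SAP 4.4 adds: "The number of active study agent injections, and the cumulative dose of study agent will be summarized by treatment group". SAP 7.1 also plans event rates per hundred subject-years through Week 52. SAP Section 7 plans no formal safety comparison.

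**The concern.** An injection-site reaction needs an injection. For this category, similar calendar time does not mean similar opportunity for the event. A child on etanercept has more than five times as many dosing occasions as a child on guselkumab, so the percentage with at least one reaction will be higher on etanercept even if each injection is equally well tolerated.

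Nothing else planned fills the gap. The only event rate is per subject-year. In the Week 52 groups, participants who started on etanercept contribute only from their first guselkumab dose, so no rate covers the etanercept period. Injection pain is scored only for placebo and guselkumab injections (SAP 7.4.2). The Week 16 injection-site reaction table is therefore the main planned view of local tolerability against the active comparator, and it could be read as a product difference when part or all of the gap comes from the schedule.

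**Working it through.** The documents state no injection-site reaction rate, so there is no planned figure to reproduce. The check derives the exposure counts and then asks what the planned percentage shows when the true risk per injection is equal.

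**Administrations before Week 16**
- Etanercept: footnote i lists the weeks without a scheduled site visit ("ie, Weeks 1, 2, 3, 5, 6, 7, 9, 10, 11, 13, 14, and 15"), which is 12. Adding the site visits at Weeks 0, 4, 8 and 12 gives 12 + 4 = 16.
- Guselkumab or placebo: Weeks 0, 4 and 12, which is 3.
- At one or two injections per dose: 16 to 32 injections for etanercept, 3 to 6 for guselkumab or placebo.

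**Independent reactions, one injection per dose.** With risk p per injection (assumed) and n injections, P(at least one) = 1 − (1 − p)^n. For p = 2%: 1 − 0.98^3 = 5.9% and 1 − 0.98^16 = 27.6%.

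| Assumed p | 3 injections | 16 injections | Ratio |
|---|---|---|---|
| 1% | 3.0% | 14.9% | 5.00 |
| 2% | 5.9% | 27.6% | 4.70 |
| 3% | 8.7% | 38.6% | 4.42 |
| 5% | 14.3% | 56.0% | 3.93 |
| 10% | 27.1% | 81.5% | 3.01 |
| 20% | 48.8% | 97.2% | 1.99 |

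As p approaches 0, the ratio approaches its ceiling of 16/3 = 5.33.

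**Different injections per dose (p from 1% to 5%)**
- 32 against 6: ratio 4.70 falling to 3.04.
- 16 against 6: 2.54 falling to 2.11.
- 32 against 3: 9.26 falling to 5.65.

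**Reactions clustered in the same children.** With a beta-binomial model and intraclass correlation ρ (assumed), P(at least one) = 1 − B(a, b + n)/B(a, b), where a = p(1 − ρ)/ρ and b = (1 − p)(1 − ρ)/ρ. For 16 against 3:
- p = 1%: ρ = 0.1 gives 9.1% and 2.7% (3.38); ρ = 0.3 gives 5.2% and 2.2% (2.32).
- p = 5%: ρ = 0.1 gives 38.4% and 13.0% (2.95); ρ = 0.3 gives 23.5% and 10.8% (2.17).

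Unequal injections and clustering were varied one at a time, not together.

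**What the added row would show.** Take the planned arm sizes of 40, 25 and 25, p = 2% and one injection per dose.
- Etanercept: 25 × 16 = 400 injections, 8 expected reactions.
- Guselkumab: 40 × 3 = 120 injections, 2.4 expected.
- Placebo: 25 × 3 = 75 injections, 1.5 expected.

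Each arm shows 2 per 100 injections, where the planned percentages would be 27.6% and 5.9%.

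**The case against.** The strongest reply is that the SAP already states the principle. With average administrations in the table, a reader sees about 16 against 3 and can make allowance. That stands in part, so it would be wrong to infer that the plan ignores exposure. But the percentage itself is not adjusted, injections are not the same as administrations, and the commitment covers most tables without naming this one. The exposure table in SAP 4.4 counts active injections only, so it gives no placebo count.

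A second reply is that the participant percentage is a proper measure. Injection frequency belongs to the regimen, and Protocol 4.1 itself names poor tolerance of weekly injections as a reason to switch from etanercept. This stands. The percentage answers a question about burden under the regimen as given, and should stay. It does not answer the per-injection question.

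Third, the stakes are limited. No test or decision rule uses this table. Etanercept is included as an efficacy benchmark, and the primary objective concerns guselkumab and does not name local tolerability against etanercept. All of this stands, and it makes the point an improvement and not a flaw in the main analysis.

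A reader might also infer that the guselkumab–placebo comparison is distorted because placebo injections are missing from SAP 4.4. The documents do not support that: both arms have the same three visits, the same weight-based volume calculation and site administration.

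Finally, a per-injection rate has weaknesses of its own. Up to 12 of the 16 etanercept doses may be given at home, and the 30-minute observation in Protocol 8.2.9 covers only injections at the site. Reactions may therefore be captured differently by arm, and the documents do not say that injections per home dose are recorded. Repeat events in one child are also correlated. These are reasons for footnotes and care, not for leaving the rate out.

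**Conclusion.** The concern holds for the etanercept contrast through Week 16. Similar follow-up does not give similar injection exposure, and no per-injection or per-administration rate is planned. At equal risk per injection of 1% to 5%, the etanercept percentage would be about 2 to 5 times that of guselkumab or placebo, and up to about 9 times at 32 against 3 injections.

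The size rests on three inputs that the documents do not give: the risk per injection, the injections per dose actually received, and the clustering of reactions within children. A reader might infer a fixed inflation of four to five times. That range needs a risk of about 1.0% to 4.7%, one injection per dose and independent reactions, and none of these can be taken from the documents. At higher risks the ratio falls further, to 1.52 at 30%. The direction was the same in every scenario checked: against etanercept.

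Guselkumab versus placebo is unaffected, and no efficacy conclusion or formal safety test depends on this. The proposed change is a cheap improvement.

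**What to change.** In SAP 7.1, keep the percentage of participants with at least one injection-site reaction as the measure of regimen burden. Beside it, add a descriptive rate of injection-site reactions per 100 injections by arm through Week 16. Use 100 administrations as the denominator where injections per home dose are not recorded.

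Show the number of injections or administrations for every arm, including placebo, in that same table. In SAP Section 7, add a sentence that similar follow-up does not mean similar injection exposure for etanercept.

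The cost is slightly more programming. Protocol 6.4 already requires a log of study intervention administered and a questionnaire for home etanercept doses, and Protocol 8.2.7 records reactions as adverse events with start and end dates and times. Two cautions belong with the row: any interval must allow for repeat events in the same child, and a footnote should say that reactions after home etanercept doses may be captured differently from those after site-administered doses.

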Of childbearing potential and practicing a highly effective method of contraception (failure rate of <1% per year when used consistently and correctly) and agrees to remain on a highly effective method while receiving study intervention and until 12 weeks after last dose - the end of relevant systemic exposure. Examples of highly effective methods of contraception are in [Appendix 3](#) (Section 10.3); however, the method selected must meet local/regional regulations/guidelines for highly effective contraception

Typical use failure rates may differ from those when used consistently and correctly. Use should be consistent with local regulations regarding the use of contraceptive methods for participants participating in clinical studies.

Note: If the childbearing potential changes after start of the study (eg, a premenarchal girl experiences menarche) or the risk of pregnancy changes (eg, a girl who is not heterosexually active becomes active), a girl must begin a highly effective method of contraception, as described above and in [Appendix 3](#) (Section 10.3).

If reproductive status is questionable, additional evaluation should be considered

8. A girl must agree not to donate eggs (ova, oocytes) for the purposes of assisted reproduction during the study and for a period of at least 12 weeks following the last dose of study intervention.

9. A girl of childbearing potential must have a negative urine pregnancy test at screening and at all visits when study intervention is to be administered.
10. A boy who is sexually active with a female of childbearing potential and who has not had a vasectomy must agree to use a barrier method of birth control (eg, either a condom [with spermicidal foam/gel/film/cream/suppository if available in their locale] or a partner with an occlusive cap [diaphragm or cervical/vault caps] plus spermicidal foam/gel/film/cream/suppository if available in their locale), during the study and for at least 12 weeks after receiving the last administration of study intervention. All boys must also agree to not donate sperm during the study and for at least 12 weeks after receiving the last administration of study intervention.
11. Criterion modified per Amendment 4.
  - 11.1. Are considered eligible according to the following TB screening criteria:
    - Have no history of latent or active TB before screening.
    - Have no signs or symptoms suggestive of active TB upon medical history and/or physical examination.

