Participants randomized to guselkumab (up to CCI [redacted] or placebo will receive a weight-based dose of study intervention at Weeks 0, 4, and 12. Participants randomized to etanercept will receive a weight-based etanercept dose up to 50 mg SC weekly through Week 15. Participants randomized to etanercept will be given the option to self-administer or have their caregiver administer at home or have the study intervention administered at the study site.

At Week 16:

- Participants initially randomized to guselkumab will be treated as follows:
 - PASI 90 responders at Week 16 will not receive any additional doses of guselkumab until they lose $\geq 50\%$ of their Week 16 PASI response, at which time they will be retreated with guselkumab followed by a dose 4 weeks later, and then guselkumab q8w thereafter through Week 52.
 - PASI 90 nonresponders at Week 16 will receive a placebo injection at Week 16 to maintain the blind and continue treatment with guselkumab q8w from Week 20 through Week 52.
- Participants initially randomized to placebo will be treated as follows:
 - PASI 90 responders at Week 16 will not receive any additional doses of study intervention until they lose $\geq 50\%$ of their Week 16 PASI response, at which time they will initiate

treatment with guselkumab SC followed by a dose 4 weeks later, and q8w thereafter through Week 52.

- PASI 90 nonresponders will initiate treatment with guselkumab at Weeks 16 and 20, and q8w thereafter through Week 52.
- Participants initially randomized to etanercept will receive their last administration of etanercept at Week 15. Irrespective of PASI response at Week 16, participants or their legally acceptable representative will be given the option, in consultation with the investigator, to initiate treatment with guselkumab at Week 20 followed by a dose 4 weeks later, and then q8w thereafter through Week 48, or discontinue from study agent administration. This option allows for participants receiving etanercept who have not attained an adequate level of efficacy or have poor tolerance for weekly injections to switch to guselkumab.

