4. **Combined Guselkumab:** all subjects as described above in the Placebo → Guselkumab, the Etanercept → Guselkumab and the Guselkumab groups.

In addition, the summaries of selected AE rates per hundred subject-years of follow-up through Week 52 will be provided.

Selected safety analyses will also be performed after retreatment with guselkumab among subjects who were randomized to guselkumab at Week 0, were PASI 90 responders at Week 16, were withdrawn from and then retreated with guselkumab.

Summaries through Week 52 in Part 2

Safety data through Week 52 will be summarized for all subjects who were enrolled in Part 2 and received at least 1 study agent administration of guselkumab. All the safety events/measurements from these subjects that occurred beginning at Week 0 will be included in this group.

Summaries through the LTE

Safety data through the LTE will be summarized for all subjects who participated in the LTE and were treated with guselkumab. All the safety events/measurements from Week 52 through the end of the study will be included in this group.

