Psoriasis rebound will be assessed during the withdrawal period for subjects withdrawn from guselkumab at Week 16. Psoriasis rebound is defined as an event of new erythrodermic or pustular psoriasis, or a PASI of $\geq 125\%$ of the baseline PASI (ie, a worsening of PASI by 25% or greater from baseline) that occurred during the withdrawal period from the time subjects are withdrawn from guselkumab at Week 16.

In addition, safety will be assessed for subjects who are withdrawn from guselkumab at Week 16 and subsequently retreated upon loss of response. These analyses will include safety categories of AE, infection, and injection site reaction within 16 weeks after retreatment.

Since safety should be assessed relative to exposure and follow-up, most AE summary tables will include average weeks of follow-up and average number of study agent administrations for each treatment group.

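### The Part 1 Week 52 Guselkumab and Combined Guselkumab AE rates mix on-drug time with the planned off-drug time of withdrawn PASI 90 responders, so the bias differs in direction by event type

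*SAP*

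**What the plan says.** **Dosing.** Through Week 16, participants randomized to guselkumab "or placebo will receive a weight-based dose of study intervention at Weeks 0, 4, and 12" (SAP 1.2; the sentence covers both blinded arms). Then "PASI 90 responders at Week 16 will not receive any additional doses of guselkumab until they lose" at least half of their Week 16 PASI response (Protocol 4.1). Protocol 6.1 provides for responders who reach Week 52 without being re-dosed.

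**Which events count.** SAP 7 defines the Guselkumab group through Week 52 as everyone randomized to and treated with guselkumab, and adds: "All the safety events/measurements from these subjects that occurred beginning at Week 0 will be included in this group". The Placebo→Guselkumab and Etanercept→Guselkumab groups count only from the first guselkumab dose. Combined Guselkumab is the union of the three. On treatment emergence, SAP 7.1 says: "Any AE occurring at or after the initial administration of study agent through the end of the trial is considered to be treatment emergent".

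**Denominator.** SAP 7 says "the summaries of selected AE rates per hundred subject-years of follow-up through Week 52 will be provided", and SAP 7.1 adds "number of events per hundred subject-years of follow-up through Week 52 will also be provided for all AEs".

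**Related safety output.** The SAP also plans:
- Week 16 tables by randomized treatment;
- a psoriasis-rebound assessment during withdrawal;
- AEs, infections and injection-site reactions within 16 weeks after retreatment;
- exposure summaries (SAP 4.4), with average follow-up and average number of administrations in most AE tables;
- a separate Part 2 summary.

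**The concern.** Safety is part of the primary objective, and these are the planned one-year safety rates for the arm randomized to guselkumab. A reader will take a rate labelled Guselkumab as the rate under guselkumab. In this arm a large share of participants may spend months without drug by design, and nothing in the Week 52 rate separates that time or the events in it.

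The SAP sets its own standard: "Since safety should be assessed relative to exposure and follow-up". The rates use follow-up alone. For efficacy the SAP does separate withdrawal from retreatment (SAP 5.5.2.1), and for PK it ends the responders' concentration summary at retreatment (SAP 8.1). It makes no such separation in the safety rates.

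The rows are also not alike. Both crossover groups start at the first guselkumab dose and are then scheduled for a dose 4 weeks later and every 8 weeks. Only the Guselkumab row contains planned drug-free time. Dividing by subject-years adjusts for length of follow-up, not for this difference in exposure.

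**Working it through.** The documents give no AE rate, exposure time or retreatment time, so there is no stated figure to reproduce. The size has to be built from the design and stated assumptions.

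**Inputs**
- N = 40 randomized to guselkumab in Part 1 (SAP 1.4).
- p = 0.70 PASI 90 responders at Week 16. This is an assumption; the two adult studies in Protocol 2.2.1 show 73.3% and 70.0%.
- Last dose before withdrawal: Week 12.
- Window w after the last dose: 12 weeks, from inclusion criterion 7 ("until 12 weeks after last dose - the end of relevant systemic exposure"), or 16 weeks. For deaths after the last dose, Protocol 8.3.1.2 uses 12 weeks and Appendix 4 uses 16.
- T = retreatment week: 32, 40 or 52 (none before Week 52). This is an assumption.
- No dropout.

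**Off-drug share of follow-up**

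f = N·p·(T − 12 − w) / (N·52), with N·p = 28 and N·52 = 2080 subject-weeks.

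| T | w = 12 (off drug from Week 24) | w = 16 (off drug from Week 28) |
|---|---|---|
| 32 | 28×8 = 224; 10.8% | 28×4 = 112; 5.4% |
| 40 | 28×16 = 448; 21.5% | 28×12 = 336; 16.2% |
| 52 | 28×28 = 784; 37.7% | 28×24 = 672; 32.3% |

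A wider set of assumptions uses p from 70.0% to 73.3%, off-drug time starting at Week 20 (the first omitted dose) or Week 24, and exponential time from Week 16 to retreatment with a median of 8 to 36 weeks, or no retreatment. It gives f from 7% to 45%.

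**Combined Guselkumab.** If all 25 placebo participants start guselkumab at Week 16 and all 25 etanercept participants at Week 20, the denominator is 2080 + 25×36 + 25×32 = 3780 subject-weeks. With w = 12 the off-drug share is 224/3780 = 5.9%, 448/3780 = 11.9% or 784/3780 = 20.7%.

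**Effect on a rate.** Off-drug events stay in the numerator, so the pooled rate is (1 − f)·(on-drug rate) + f·(off-drug rate). With RR = on-drug rate / off-drug rate:

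pooled / on-drug = 1 − f(1 − 1/RR)

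If the event cannot occur off drug, this becomes 1 − f. For w = 12:

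| f | no events off drug | RR = 2 | RR = 1 | RR = 0.5 |
|---|---|---|---|---|
| 10.8% | 0.89 | 0.95 | 1.00 | 1.11 |
| 21.5% | 0.78 | 0.89 | 1.00 | 1.22 |
| 37.7% | 0.62 | 0.81 | 1.00 | 1.38 |

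The first column fits events that need an injection. The last fits events more frequent off drug, plausibly worsening psoriasis. The RR values are illustrative.

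**The case against.** **Other tables already help.** The only concurrently controlled safety comparison ends at Week 16, before any withdrawal. The crossover rows and Part 2 have no planned drug-free interval. Rebound is assessed specifically off drug, and a post-retreatment analysis is specified. A reader might infer that the plan ignores the withdrawal period altogether; the rebound assessment shows otherwise. All of this is useful context, but none of it changes the Week 52 rates or gives an on-treatment rate. Apart from rebound, no table separates off-drug events. Part 2 has a stated minimum of only 10 participants.

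**The rates may hardly move.** A reader might infer that every AE rate in this group is diluted. The documents do not support that: off-drug events are counted too, and at RR = 1 nothing changes. For adults, Protocol 2.2.1 and 2.3.1 report AE and infection frequencies comparable with placebo through Week 16, so an RR of 2 has no support in the documents. This stands. The case rests on mixing of unknown size, not on a known hidden excess.

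**Injection-site reactions.** SAP 7.1 plans counts and percentages for them. No subject-year rate is explicitly promised for that category, so the example applies only if one is given.

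**The window.** The 12 weeks come from a contraception criterion, not from a safety-attribution rule. This stands, and is why both windows are shown.

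**Counting everything is defensible.** Withdrawal and retreatment is the assigned strategy and serves secondary objectives. All-follow-up counting also keeps late-onset events in view, and no formal safety comparison is planned. This justifies keeping the existing tables; it does not make their rates on-drug rates.

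**Conclusion.** The point holds as one of mixing. The Week 52 Guselkumab and Combined Guselkumab rates average on-drug and off-drug experience, and the direction of the error depends on the event. It is downward for AEs more frequent on drug (with certainty for injection-site reactions, if a rate is reported), nil for unrelated AEs, and upward for AEs more frequent off drug. Because the direction varies, a reader cannot correct for it from the planned tables. The Guselkumab row is also not exposure-comparable with the two crossover rows.

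The off-drug share plausibly runs from about 5% to 38% of the Guselkumab group's follow-up across the two windows. That rests on adult response rates, full follow-up and assumed retreatment times. The top of the range requires that no responder is re-dosed before Week 52.

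No efficacy test, type I error or Week 16 safety comparison is affected. The change is worth making because it is cheap and the one-year pediatric safety rates bear on the primary objective.

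**What to change.** In SAP 7 and 7.1, add for the Guselkumab and Combined Guselkumab groups through Week 52:

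- **On-treatment rates** per 100 subject-years, from first guselkumab dose to a pre-specified window after the most recent dose, restarting at retreatment. Use, for example, 12 weeks, with 16 weeks as a sensitivity analysis.
- **Off-treatment events and rates**, from the end of that window until retreatment or Week 52.

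Give both for AEs, SAEs, infections and injection-site reactions. Keep the all-follow-up tables alongside, so that events arising long after a dose stay visible.

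**Cost.** SAP wording, one on/off-treatment variable derived from dosing dates already collected, and a few extra tables. No new data and no change in conduct. Each split rate has fewer subject-years and a wider interval: with the 12-week window, on-treatment time in the Guselkumab group falls from 40 subject-years to (2080 − 224)/52 = 35.7, (2080 − 448)/52 = 31.4 or (2080 − 784)/52 = 24.9 in the three cases above.
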